10.1 Definition of AE

AE Definition

An AE is any untoward medical occurrence in a clinical study participant, temporally associated with the use of a study intervention, whether or not considered related to the study intervention. NOTE: An AE can therefore be any unfavorable and unintended sign (including an abnormal laboratory finding), symptom, or disease (new or exacerbated) temporally associated with the use of a study intervention.

Events Meeting the AE Definition

Any abnormal laboratory test results (hematology, clinical chemistry, or urinalysis) or other safety assessments (e.g., ECG, radiological scans, vital signs measurements), including those that worsen from baseline, considered clinically significant in the medical and scientific judgment of the investigator (i.e., not related to progression of underlying disease).Exacerbation of a chronic or intermittent pre-existing condition including either an increase in frequency and/or intensity of the condition.New conditions detected or diagnosed after study intervention administration even though it may have been present before the start of the study.• Signs, symptoms, or the clinical sequelae of a suspected intervention- intervention interaction.Signs, symptoms, or the clinical sequelae of a suspected overdose of either study intervention or a concomitant medication. Overdose per se will not be reported as an AE/SAE unless it is an intentional overdose taken with possible suicidal/selfharming intent. Such overdoses should be reported regardless of sequelae."Lack of efficacy" or "failure of expected pharmacological action" per se will not be reported as an AE or SAE. Such instances will be captured in the efficacy assessments. However, the signs, symptoms, and/or clinical sequelae resulting from lack of efficacy will be reported as AE or SAE if they fulfill the definition of an AE or SAE.The signs, symptoms, and/or clinical sequelae resulting from lack of efficacy will be reported as AE or SAE if they fulfill the definition of an AE or SAE. "Lack of efficacy" or "failure of expected pharmacological action" also constitutes an AE or SAE.

Events NOT Meeting the AE Definition

- Any clinically significant abnormal laboratory findings or other abnormal safety assessments which are associated with the underlying disease, unless judged by the investigator to be more severe than expected for the participant's condition.
- The disease/disorder being studied or expected progression, signs, or symptoms of the disease/disorder being studied, unless more severe than expected for the participant's condition.
- Medical or surgical procedure (e.g., endoscopy, appendectomy): the condition that leads to the procedure is the AE.
- Situations in which an untoward medical occurrence did not occur (social and/or convenience admission to a hospital).
- Anticipated day-to-day fluctuations of pre-existing disease(s) or condition(s) present or detected at the start of the study that do not worsen.

10.2 Definition of SAE

An SAE is defined as any serious adverse event that, at any dose:	
a.	Results in death
b.	Is life-threatening The term 'life-threatening' in the definition of 'serious' refers to an event in which the participant was at risk of death at the time of the event. It does not refer to an event, which hypothetically might have caused death, if it were more severe.
c.	Requires inpatient hospitalization or prolongation of existing hospitalization 
 In general, hospitalization signifies that the participant has been admitted (usually involving at least an overnight stay) at the hospital or emergency ward for observation and/or treatment that would not have been appropriate in the physician's office or outpatient setting. Complications that occur during hospitalization are AE. If a complication prolongs hospitalization or fulfills any other serious criteria, the event is serious. When in doubt as to whether "hospitalization" occurred or was necessary, the AE should be considered serious. Hospitalization for elective treatment of a pre-existing condition that did not worsen from baseline is not considered an AE.
d.	Results in persistent or significant disability/incapacity 
 The term disability means a substantial disruption of a person's ability to conduct normal life functions. This definition is not intended to include experiences of relatively minor medical significance such as uncomplicated headache, nausea, vomiting, diarrhea, influenza, and accidental trauma (e.g. sprained ankle) which may interfere with or prevent everyday life functions but do not constitute a substantial disruption.
e.	Is a congenital anomaly/birth defect
f.	Is a suspected transmission of any infectious agent via an authorised medicinal product
g.	Other situations: 
 Possible Hy's Law case: ALT\geq3xULN AND total bilirubin \geq2xULN ($>35\%$ direct bilirubin) or international normalized ratio (INR) >1.5 must be reported as SAE Medical or scientific judgment should be exercised by the investigator in deciding whether SAE reporting is appropriate in other situations such as significant medical events that may jeopardize the participant or may require medical or surgical intervention to prevent one of the other outcomes listed in the above definition. These events should usually be considered serious. Examples of such events include invasive or malignant cancers, intensive treatment for allergic bronchospasm, blood dyscrasias, convulsions, or development of intervention dependency or intervention abuse.

10.3 Definition of Study treatment related AEs

It may also be referred to as Adverse Drug Reaction (ADR).

Study treatment related AE Definition

A response to a medicinal product which is noxious and unintended.

Response in this context means that a causal relationship between a medicinal product and an adverse event is at least a reasonable possibility.

An adverse reaction, in contrast to an adverse event, is characterized by the fact that a causal relationship between a medicinal product and an occurrence is suspected.

10.4 Recording and Follow-Up of AE and SAE

AE and SAE Recording

- When an AE/SAE occurs, it is the responsibility of the investigator to review all documentation (e.g. hospital progress notes, laboratory, and diagnostics reports) related to the event.
- The investigator will then record all relevant AE/SAE information.
- It is not acceptable for the investigator to send photocopies of the participant's medical records to GSK in lieu of completion of the GSK required form.
- There may be instances when copies of medical records for certain cases are requested by GSK. In this case, all participant identifiers, with the exception of the participant number, will be redacted on the copies of the medical records before submission to GSK.
- The investigator will attempt to establish a diagnosis of the event based on signs, symptoms, and/or other clinical information. Whenever possible, the diagnosis (not the individual signs/symptoms) will be documented as the AE/SAE.

Assessment of Intensity

- The investigator will make an assessment of intensity for each AE and SAE reported during the study and assign it to 1 of the following categories:
- Mild: An event that is easily tolerated by the participant, causing minimal discomfort and not interfering with everyday activities.
- Moderate: An event that causes sufficient discomfort and interferes with normal everyday activities.
- Severe: An event that prevents normal everyday activities. An AE that is assessed as severe should not be confused with an SAE. Severe is a category utilized for rating the intensity of an event; and both AE and SAE can be assessed as severe.

- An event is defined as 'serious' when it meets at least 1 of the predefined outcomes as described in the definition of an SAE, NOT when it is rated as severe.

Assessment of Causality

- The investigator is obligated to assess the relationship between study intervention and each occurrence of each AE/SAE.
- A "reasonable possibility" of a relationship conveys that there are facts, evidence, and/or arguments to suggest a causal relationship, rather than a relationship cannot be ruled out.
- The investigator will use clinical judgment to determine the relationship.
- Alternative causes, such as underlying disease(s), concomitant therapy, and other risk factors, as well as the temporal relationship of the event to study intervention administration will be considered and investigated.
- The investigator will also consult the Investigator's Brochure (IB) and/or Product Information, for marketed products, in his/her assessment.
- For each AE/SAE, the investigator must document in the medical notes that he/she has reviewed the AE/SAE and has provided an assessment of causality.
- There may be situations in which an SAE has occurred and the investigator has minimal information to include in the initial report to GSK. However, it is very important that the investigator always make an assessment of causality for every event before the initial transmission of the SAE data to GSK.
- The investigator may change his/her opinion of causality in light of follow-up information and send an SAE follow-up report with the updated causality assessment.
- The causality assessment is one of the criteria used when determining regulatory reporting requirements.

Follow-up of AE and SAE

- The investigator is obligated to perform or arrange for the conduct of supplemental measurements and/or evaluations as medically indicated or as requested by GSK to elucidate the nature and/or causality of the AE or SAE as fully as possible. This may include additional laboratory tests or investigations, histopathological examinations, or consultation with other health care professionals.
- If a participant dies during participation in the study or during a recognized follow up period, the investigator will provide GSK with a copy of any post-mortem findings including histopathology.
- New or updated information will be recorded in the originally submitted documents.

- The investigator will submit any updated SAE data to GSK within 24 hours of receipt of the information.

10.5 Reporting of SAE to GSK

SAE Reporting to GSK via Electronic Data Collection Tool

- The primary mechanism for reporting SAE to GSK will be the electronic data collection tool.
- If the electronic system is unavailable, then the site will use the paper SAE data collection tool (see next section) to report the event within 24 hours.
- The site will enter the SAE data into the electronic system as soon as it becomes available.
- The investigator or medically-qualified sub-investigator must show evidence within the eCRF (e.g., check review box, signature, etc.) of review and verification of the relationship of each SAE to IP/study participation (causality) within 72 hours of SAE entry into the eCRF.
- After the study is completed at a given site, the electronic data collection tool will be taken off-line to prevent the entry of new data or changes to existing data.
- If a site receives a report of a new SAE from a study participant or receives updated data on a previously reported SAE after the electronic data collection tool has been taken off-line, then the site can report this information on a paper SAE form (see next section) or to the [X/medical monitor/SAE coordinator] by telephone.
- Mail to [contact] to report SAE.

SAE Reporting to GSK via Paper Data Collection Tool

- Facsimile transmission of the SAE paper data collection tool is the preferred method to transmit this information to the [X/medical monitor or the SAE coordinator].
- In rare circumstances and in the absence of facsimile equipment, notification by telephone is acceptable with a copy of the SAE data collection tool sent by overnight mail or courier service.
- Initial notification via telephone does not replace the need for the investigator to complete and sign the SAE data collection tool within the designated reporting time frames.
- Mail to [contact] to report SAE

11 APPENDIX 4: COLLECTION OF PREGNANCY INFORMATION

Definitions

Woman of Childbearing Potential (WOCBP)

A woman is considered fertile following menarche and until becoming post-menopausal unless permanently sterile (see below).

Women in the following categories are not considered WOCBP

1. Premenarchal
2. Premenopausal female with ONE of the following:
 - Documented hysterectomy
 - Documented bilateral salpingectomy
 - Documented bilateral oophorectomy
3. Postmenopausal female
 - A postmenopausal state is defined as no menses for 12 months without an alternative medical cause.
 - Females on HRT must have physician confirmation of postmenopausal status prior to study enrolment.

Female Participants who become pregnant

- Investigator will collect pregnancy information on any female participant, who becomes pregnant while participating in this study.
- Information will be recorded on the appropriate form and submitted to GSK within 24 hours of learning of a participant's pregnancy.
- Participant will be followed to determine the outcome of the pregnancy. The investigator will collect follow up information on participant and neonate, which will be forwarded to GSK.
- Generally, follow-up will not be required for longer than 6 to 8 weeks beyond the estimated delivery date.
- Any termination of pregnancy will be reported, regardless of foetal status (presence or absence of anomalies) or indication for procedure.
- While pregnancy itself is not considered to be an AE or SAE, any pregnancy complication or elective termination of a pregnancy will be reported as an AE or SAE.

A spontaneous abortion is always considered to be an SAE and will be reported as such.

- Any SAE occurring as a result of a post-study pregnancy which is considered reasonably related to the study treatment by the investigator, will be reported to GSK as described in Section 5.2. While the investigator is not obligated to actively seek this information in former study participants, he or she may learn of an SAE through spontaneous reporting.

Any female participant who becomes pregnant while participating will be withdrawn from the study.

Signature Page for 217658 TMF-15637673 v2.0

Reason for signing: Approved	Name: PPD
	Role: Approver
	Date of signature: 27-Jan-2023 13:03:21 GMT+0000

Signature Page for TMF-15637673 v2.0

6.3.1. General.....	17

CONFIDENTIAL

6.3.2. E.D. Data	17
6.4. Appendix 4 Handling of Missing or Partial Dates.....	18
6.5. References	19

Version history

SAP Version	Approval Date	Protocol Version (Date) on which SAP is Based	Change	Rationale
SAP 1.0	10 Nov 2023	Original (02Feb2022)	Not Applicable	Original version
SAP amendment 1.0	10 Nov 2023	Amend (27Jan2023)	
Add 'to evaluate the proportion of patients achieving health status response with Trelegy.' as the third secondary objective.
 
Add an additional secondary outcome to see CAT score change at week 4.
	To align with Protocol Amendment.
SAP amendment 1.0	10 Nov 2023	Amend (27Jan2023)	
Remove Interim analysis in the section of '1.2 study design'.
 
Change the name of the Interim Analysis section to additional analysis for license renewal.
	To add flexibility to provide data for license renewal.
SAP amendment 1.0	10 Nov 2023	Amend (27Jan2023)	
Inverse-probability weighted mixed model for repeated measures (MMRM) was updated and written into the primary analysis.
	The MMRM may provide additional insights to the primary endpoint.

SAP Version	Approval Date	Protocol Version (Date) on which SAP is Based	Change	Rationale
SAP amendment 1.0	10 Nov 2023	Amend (27Jan2023)	Update the baseline and post-baseline covariates for the primary analysis.	Further specification of covariates used in IPW and MMRM.
SAP amendment 1.0	10 Nov 2023	Amend (27Jan2023)	Delete the description of the process of filtering covariates. Update the description of using MMRM model to analyze the change from baseline in CAT score. Add the description that the week 4 and week 12 may have different IPW weights.	For clarification
SAP amendment 1.0	10 Nov 2023	Amend (27Jan2023)	Update the description of sensitivity analysis and indicate the covariates included in the model.	The description of the method of primary analysis changes.
SAP amendment 1.0	10 Nov 2023	Amend (27Jan2023)	Delete the exploratory endpoint 'Change from baseline of FEV1/FVC ratio at week 12'.	Correction.

1. INTRODUCTION

The purpose of this SAP is to describe the planned analyses to be included in the CSR for Study 217658. It describes the rules and conventions to be used in the analysis and presentation of data, the data to be summarised and analysed, including specificities of the statistical analyses to be performed.

1.1. Objectives, Estimands and Endpoints

Objectives	Endpoints
Primary	

 The primary objective of this study is to evaluate the effectiveness of Trelegy on health status in patients with symptomatic COPD at week 12. 	
 Change from baseline of CAT score at week 12
Secondary	

 to evaluate the effectiveness of Trelegy on dyspnea in patients with symptomatic COPD at week 12. to evaluate the effectiveness of Trelegy on lung function in patients with symptomatic COPD at week 12. to evaluate the proportion of patients achieving health status response with Trelegy. to evaluate the effectiveness of Trelegy on health status in patients with symptomatic COPD at week 4. 	
 Change from baseline of Modified Medical Research Council (mMRC) at week 12 Change from baseline of pre-dose FEV1 at week 12 Proportion of CAT responder (defined as ≥ 2 unit decrease from baseline) at week 12 Change from baseline of CAT score at week 4
Exploratory	

 to evaluate the effectiveness of Trelegy on lung function in patients with symptomatic COPD 	
 Change from baseline of Forced Vital Capacity (FVC), Forced Expiratory Flow at the 25 and 75% (FEF_{25-75}), Inspiratory Capacity (IC) at week 12

Objectives	Endpoints
Safety 
• The safety objective is to collect the safety information of participants using Trelegy.	
• Trelegy related AEs• SAEs• AEs that lead to the discontinuation of Trelegy

Primary estimand refers to Section 4.2.1.

1.2. Study Design

Overview of Study Design and Key Features	
Design Features	
This is a 12-week, prospective, open label, single cohort study. The enrolled participants will be those who are symptomatic under COPD maintenance treatments, and newly prescribed with Trelegy under the discretion by clinical physicians.
 
The study applies a single cohort design to evaluate the effectiveness following 12-week treatment with Trelegy by comparison to baseline data, which can reflect the benefits (i.e., CAT score and FEV1, etc.) of patients who remain symptomatic with their prior maintenance treatment. The decision to prescribe Trelegy shall be independent to the study with medical records providing documentation of a Trelegy prescription.
 
The prospective data collection starts from Visit 1 when Trelegy is taken by patients for the first dose. The participants will complete the CAT score at Visit 1, Visit 2 and Visit 3 or early discontinuation/withdrawal visit (E.D.), and the mMRC at Visit 1 and Visit 3 or E.D. The participants' pulmonary function test will be assessed at Visit 1 and Visit 3 or E.D.. The investigators will record Trelegy-related adverse events (AEs), serious adverse events (SAEs) and AEs that lead to withdrawal from Trelegy.

Study Treatment	All patients will receive Trelegy (FF/UME/CVI ELLIPTA 100/62.5/25 µg) according to the local SmPC. Participants are expected to inhale one dose in the morning from the Trelegy Ellipta at approximately the same time each day for 12 weeks after enrolment.

2. STATISTICAL HYPOTHESES

The primary objective of this study is to evaluate the effectiveness following 12-week treatment with Trelegy by comparison to baseline data. There are no formal hypothesis tests associated with this objective and no formal significance tests.

2.1. Multiplicity Adjustment

Not applicable.

3. ANALYSIS SETS

For purposes of analysis, the following populations are defined:

Analysis Set	Definition / Criteria	Analyses Evaluated
Screened	All participants who were prescreened or screened, i.e. those having signed the informed consent.	Disposition
Enrolled	All participants who entered the study, i.e. those having passed the screening procedure.	Disposition
Full Analysis Set (FAS)	All participants who enrolled into the study and take at least one dose of Trelegy	
 • Disposition • Demographic and baseline characteristic • All effectiveness analyses • All safety analyses

4. STATISTICAL ANALYSES

4.1. General Considerations

4.1.1. General Methodology

Unless otherwise specified, continuous data will be summarized using descriptive statistics: n, mean, standard deviation (std), median, minimum and maximum. Categorical data will be summarized as the number and percentage of participants in each category.

Confidence intervals will use 95% confidence levels unless otherwise specified.

4.1.2. Baseline Definition

For all endpoints, the baseline value will be the latest pre-dose of Trelegy assessment with a non-missing value, including those from unscheduled visits. If time is not collected, Day 1 assessments are assumed to be taken prior to first dose and used as baseline, and values at scheduled visit have higher priority than the ones at the unscheduled visits if the two records are on the same day.

Unless otherwise stated, if baseline data is missing, no derivation and/or imputation will be performed and baseline will be set as missing.

All baseline values will be referred to as 'Baseline' in the summary outputs.

4.2. Primary Endpoint Analyses

4.2.1. Definition of estimand

The primary clinical question of interest is: what is the change from baseline in CAT score at week 12, regardless of receiving a new COPD maintenance therapy or treatment discontinuation.

The estimand is described by the following attributes:

- Population: Symptomatic Chinese COPD participants who are receiving COPD maintenance treatment
- Treatment condition: Trelegy (FF/UME/CVI ELLIPTA 100/62.5/25 µg) one dose daily, inhaled
- Variable: change from baseline of CAT score at week 12.
- Intercurrent events:
 - Receiving other COPD maintenance therapy is addressed by the treatment policy strategy.
 - Treatment discontinuation due to any reason is addressed by the treatment policy strategy.
- Summary measure: average change from baseline in CAT score at week 12.

Rationale: Interest lies in the treatment effect at week 12 in the real-world setting, maybe confounded by other COPD maintenance therapies or the event of treatment discontinuation due to any reason. Therefore, treatment policy strategy is employed to handle the intercurrent events of receiving a new COPD maintenance therapy and treatment discontinuation due to any reason as it reflects the clinical practice.

The COPD Assessment Test (CAT) is a validated 8-item questionnaire developed for use in routine clinical practice to measure the health status of patients with COPD [Jones, 2009; Jones, 2012]. Participants rate their experience on a 6-point scale (Protocol Appendix 1-1), ranging from 0 (no impairment) to 5 (maximum impairment) with a scoring range of 0-40. Higher scores indicated greater disease impact.

In the derivation of CAT total score, the score of an item at a visit is set as the average of the other non-missing items when only this item is missing at that visit.

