3.7 Sample Size Calculations

3.7.1 Statistical assumptions

INTREPID study [study 206854 China CSR GSK Document Number [2019N418769_00](#)] showed that in the real world setting 19% participants had early withdrawn from the Trelegy treatment prior to week 24. Considering the difference in the China clinical practice and study designs, it is assumed that 79% enrolled participants would complete 12 weeks of Trelegy treatment with no intercurrent events, 20% would have the intercurrent event of receiving a new COPD maintenance therapy, 1% would have the intercurrent event of treatment discontinuation.

Based on results from a few studies, i.e., IMPACT [[Lipson](#), 2018; study CTT116855 China CSR GSK Document Number [2018N356723_00](#)], INTREPID [study 206854 China CSR GSK Document Number [2019N418769_00](#)] and one randomized controlled trial (RCT) [[Bansal](#), 2021], it is assumed that a decrease of 2 in the primary endpoint at week 12 will be observed in this study with a common standard deviation of 7 ([Table 2](#)).

Table 2 Assumptions for the primary endpoint

Proportion of each type of participants	Primary endpoint		
	Mean	Standard deviation	
Participants with no intercurrent events	79%	-2	7
Participants receiving other COPD maintenance therapy	20%	-2	7
Participants with treatment discontinuation	1%	0	7
Total	100%	-1.98	7.003

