3.7.2 Sample size consideration

A sample size of 460 is planned. With the aforementioned assumptions in [Table 1](#), the sample size would be able to provide a half-width ranging from 0.64 to 0.73 for the 95% confidence interval (CI) of the inverse probability weighted mean of the change from baseline in CAT score at week 12 in the primary analysis under different missingness scenarios ([Table 3](#)).

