4.2.3. Sensitivity analyses

Sensitivity analysis will be conducted using a MMRM with the covariates of smoking status, CAT score at baseline, visit, the interaction of CAT score at baseline*visit to derive the point estimate and the standard error of change from the baseline in the CAT score, but in which the

missing data in the primary endpoint will be imputed using monotone linear regression multiple imputation under missing at random assumption, for participants with no intercurrent events, receiving other COPD maintenance therapy, with treatment discontinuation, separately if data permits, otherwise may be imputed for the pooled groups, using the observed factors, i.e. the baseline covariates and the post-baseline covariates by the time of missingness.

The missing values in the covariate may be imputed with information by time of its missingness if deemed necessary.

At least 1000 datasets will be generated which include both observed and imputed values for the covariates. The MMRM estimates for the primary endpoint as well as the corresponding standard errors from each complete dataset will be combined using the Rubin's rule.

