4.3. Secondary Endpoints Analyses

4.3.1. Secondary endpoints

The analysis approach for the below secondary endpoints is analogous to the primary analysis and the sensitivity analyses for the primary endpoint:

- Change from baseline of Modified Medical Research Council (mMRC) at week 12
- Change from baseline of pre-dose FEV₁ at week 12
- Proportion of CAT responder (defined as ≥ 2 unit decrease from baseline) at week 12
- Change from baseline of CAT score at week 4

In the analysis for the proportion of CAT responder (defined as ≥ 2 unit decrease from baseline) at week 12, the considerations follow:

- Summary measure is the proportion of participants having ≥ 2 unit decrease from baseline at week 12.
- The response status of a participant at a visit is set to missing if his/her CAT score at baseline or at the visit is missing.
- The IPW weights used for primary endpoint were applied here to estimate the proportion of CAT responder at Week 12.

The missingness of the change from baseline in CAT score at week 4 will be modelled analogously as the primary analysis but with the covariates collected before week 4. The missing values in the covariates may be imputed with information by time of its missingness. The IPW weights are applied at the observation level, thus the observations for a same subject with available change from baseline in CAT score values at the week 4 and week 12 may have different weights.

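### Death has no intercurrent-event strategy of its own, so deaths before Week 12 are handled as missing data and about 40% to 50% of them are in effect counted as CAT responders

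*SAP*

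**What the plan says.** - **Estimand.** SAP 4.2.1 and Protocol 3.8.2.1 carry the same list of two intercurrent events: a switch to other COPD maintenance therapy, and stopping Trelegy. Both are under treatment policy. For the second: "Treatment discontinuation due to any reason is addressed by the treatment policy strategy". Death does not appear.
- **Primary analysis (SAP 4.2.2).** A logistic model classes each Week 12 change as observed or missing, and observed values are weighted by the inverse probability of being observed. Intercurrent event status enters as three classes: none, switched, and stopped for another reason. None is for death.
- **Sensitivity analysis (SAP 4.2.3).** Here, "missing data in the primary endpoint will be imputed using monotone linear regression multiple imputation under missing at random assumption". This is done by intercurrent event class if the data allow and otherwise with classes pooled.
- **Responder endpoint (SAP 4.3.1; same rule in Protocol 3.8.2.2).** "The response status of a participant at a visit is set to missing if his/her CAT score at baseline or at the visit is missing". SAP 4.3.1 reuses the primary weights.
- **Early-discontinuation (E.D.) data (SAP 6.3.2).** An E.D. value after Day 55 serves as the Week 12 value. At or before Day 55, Week 12 is missing.
- **Where death does appear.** Protocol Appendix 3 treats it as a seriousness criterion and a follow-up matter. No expected death rate is given.

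**The concern.** Treatment policy uses the Week 12 value whatever happened before it. That works for a participant who stops Trelegy and stays in the study. It has no meaning for one who has died, and no other rule in the SAP's analysis or derivation sections covers that case. Death is therefore handled as ordinary missing data, and living participants supply the outcome.

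The responder endpoint is where this matters most. A death is a clear failure to respond, yet the stated rule never records it as one, so any error is in the favourable direction. The sensitivity analysis shares the feature and cannot reveal it. For the means, the plan does not say whom the Week 12 figure describes. If deaths occur, the choice would have to be made after they are known.

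**Working it through.** **Inputs**
- Protocol 3.7.2: "A sample size of 460 is planned".
- Protocol 3.7.1: "a decrease of 2 in the primary endpoint at week 12 will be observed in this study with a common standard deviation of 7".
- Protocol 3.7.1: "20% would have the intercurrent event of receiving a new COPD maintenance therapy, 1% would have the intercurrent event of treatment discontinuation". The remaining 79% have no event.
- Protocol Table 2: mean change −2 with no event or after a switch, 0 after discontinuation, SD 7 throughout.
- Protocol Table 3, missing at Week 12 by class (none / switch / discontinued): 5% / 30% / 50% in scenario 2, and 10% / 50% / 70% in scenario 3.
- SAP 4.1.1: "Confidence intervals will use 95% confidence levels unless otherwise specified".
- Responder: a CAT decrease of at least 2.
- Death rate: not in the documents. I assume 0.5% to 2%, or about 2 to 9 of 460.

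**Step 1. Reproduce the plan's precision.**
- Mixture mean = 0.79 × (−2) + 0.20 × (−2) + 0.01 × 0 = −1.98. Mixture SD = 7.003. Both match Table 2.
- Weighted half-width = 1.96 × √{ Σ [p/(1 − missing)] × [7² + (class mean + 1.98)²] / 460 }.
- Results for scenarios 1, 2 and 3 are 0.640, 0.683 and 0.733. The protocol prints 0.64, 0.69 and 0.73. The middle figure agrees within 1%. The point below does not affect these figures.

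**Step 2. Responder probability in the group that stands in for the dead.** With normal changes, q = Φ((−2 − mean)/7). Because CAT is normally a whole number, I also use a cut of −1.5.

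| Stand-in group | Mean | q, cut −2 | q, cut −1.5 |
|---|---|---|---|
| No event, or switched | −2 | 0.500 | 0.528 |
| Classes pooled | −1.98 | 0.499 | 0.527 |
| Discontinued | 0 | 0.388 | 0.415 |

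Varying the SD from 6.5 to 7.5 (the range in Protocol Table 4) changes these by about one percentage point or less.

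**Step 3. Which row applies.** The SAP does not say which class a death on treatment enters. Stopped for another reason is the natural reading. That class expects 0.01 × 460 = 4.6 participants, with a Week 12 CAT in 4.6 × 0.50 = 2.3 (scenario 2) or 4.6 × 0.30 = 1.4 (scenario 3). Weights that depend on this class would lean on one or two living people, with q about 39% to 42%. Separate imputation is unlikely to be feasible with so few, and pooling gives q about 50% to 53%.

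**Step 4. Effect on the responder proportion.** Let d be the share who die before Week 12 without a usable E.D. value. The plan in effect adds d × q responders. Counting death as non-response adds none. The overstatement is d × q, or 0.39 to 0.53 points per 1% of deaths.

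| Deaths of 460 | d | d × 0.388 | d × 0.528 |
|---|---|---|---|
| 2 | 0.43% | 0.17 points | 0.23 points |
| 5 | 1.09% | 0.42 points | 0.57 points |
| 9 | 1.96% | 0.76 points | 1.03 points |

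The 95% CI half-width of a proportion of 0.499 with 460 participants and no missing data is 1.96 × √(0.499 × 0.501/460) = 0.0457, or 4.6 points.

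**Step 5. Effect on the mean CAT change.** Giving the dead a change of 0 rather than −2 moves the mean by 2d: 0.009 for 2 deaths and 0.039 for 9. The half-width is at least 0.64.

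**The case against.** The strongest case on the other side is that nothing turns on this.

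- **No decision rule.** The study has one cohort and no threshold to meet: "There are no formal hypothesis tests associated with this objective and no formal significance tests". There is no between-arm contrast for mortality to distort. This stands and limits the weight of the point.
- **Few deaths are likely.** Follow-up is 12 weeks, and Protocol 3.4.2 excludes low 3-month survival, unstable COPD, and a need for more than 3 L/min oxygen at rest. This stands. Nine deaths would also exceed the whole planned discontinuation class of 4.6. If that entire class died, the overstatement would be 1% × 0.388 to 0.415, or about 0.4 points. The upper end of my range therefore needs more deaths than the plan's own figures leave room for in that class.
- **Deaths are not hidden.** SAP 4.5.1 tabulates SAEs on and after treatment, and SAP 6.1.1 summarises reasons for stopping. This is true, but it does not correct the responder figure.

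Three stronger readings are tempting, and the documents do not support them.

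- **Weighting is invalid because the dead have no chance of being observed.** That holds only after conditioning on death, which is not a covariate in the SAP 4.2.2 model. Given the listed covariates, the probability need not be zero. The defect is in what is being estimated.
- **Both missing-data methods give the dead a score.** Weighting assigns none. It lets observed participants stand in, with the same effect on the estimate. Only the multiple imputation creates a value.
- **Half of all deaths count as responders.** That holds for the pooled, no-event and switched groups. The plan's discontinuation class gives 39% to 42%. A participant with an E.D. CAT after Day 55 who then dies contributes a real score.

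**Conclusion.** The point holds as a gap in the estimand and in the responder rule. Death falls by default under a strategy that cannot apply to it, and the responder endpoint treats it as missing rather than as failure. On the plan's assumptions about 40% to 50% of such deaths are in effect credited as response. This overstates the responder proportion by about 0.4 to 0.5 points per 1% of participants who die, or about 0.2 to 1 point at an assumed 0.5% to 2% mortality. The CI half-width is about 4.6 points.

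The result rests on normally distributed changes, the means and SD in Protocol Table 2, and a death rate that is purely my assumption. The effect on the mean CAT change is negligible in size. A reader might infer that the study's conclusions are distorted, but these figures do not show that. The correction is worth making because the error has one direction and the remedy is cheap.

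**What to change.** Amend SAP 4.2.1 and 4.3.1, and record the change in SAP 4.8 as a departure from the protocol.

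1. Name death as a separate intercurrent event.
2. In the responder endpoint, count any death before Week 12 as non-response with weight 1, in both the weighted and the imputation analyses, including when an E.D. CAT after Day 55 exists. State which day counts as Week 12, since Visit 3 is Day 84 with a window of 10 days either side.
3. For the CAT, mMRC and spirometry means, state that the estimate describes participants alive at Week 12, and leave deaths out of the missingness and imputation models. This should not be labelled a while-alive estimate, which would normally use values before death. The choice of strategy for the means is a trade-off, and a survivor mean is simple to explain in a single cohort.
4. Report the number of deaths beside each estimate.

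Protocol 3.2.1 ends data collection after the E.D. visit, so some deaths after withdrawal may not be known. The rule can cover only recorded deaths, and the SAP should say so.

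The cost is some SAP wording, one derivation rule and a slightly less favourable responder figure. The sample size does not change, and recording the change in SAP 4.8 avoids a protocol amendment.
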